#### 8.2 Objectives:

Primary objective

- to quantify the cumulative incidence (risk and rate) of major bleeding according to the TIMI classification of non-CABG Related Bleeding (Table 1) occurring in the 12 week observation period, overall and stratified by the following bleeding sites:
  - o Intracranial,
  - o Gastrointestinal
  - o Urogenital

Secondary objectives

- 1. Advancing the understanding of the patient population prescribed rivaroxaban in combination with standard oral antiplatelet therapy for ACS in the secondary care hospital setting including drug utilisation characteristics
- 2. Describing changes of health profile of patients, assessment of adherence, number of indication related episodes (ACS related events), plus any alterations of the treatment programme in respect of antiplatelet and anticoagulant therapy during the 12 week study observation period
- 3. Quantifying the risk of other major (in any other site not specified in the primary objective) or minor bleeding outcomes (in any site) reported in the 12 week observation period overall (Tables 1 and 2) and, if number of reports are sufficient, in patient subgroups of special interest in first 12 weeks of treatment under conditions of the routine secondary care hospital setting in England and Wales.

Both the primary and secondary objectives relate to the rivaroxaban cohort and the contextual comparator (reference) cohort.

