#### 9.3 Variables

#### 9.3.1 Eligible patient baseline information

For all eligible patients invited to participate, the following anonymised information will be collected on a baseline questionnaire from the specialist HCP using information contained within medical charts:

- Demographic characteristics (age, gender)
- Setting of first prescription- (e.g. inpatient hospital ward, outpatient clinic)
- Reasons for prescribing (clinical judgement, recommendation from NICE, expert committee guidelines, trust formulary committee guidelines)
- Which anticoagulant/antiplatelet regimen was prescribed and start date
- Clinical condition requiring anticoagulant/antiplatelet therapy (indication) and details of the clinical condition (e.g. STEMI, NSTEMI)
- Any prior anticoagulant/antiplatelet treatment
- Risk factors for bleeding at baseline (e.g. creatinine, white cell count, anaemia, presentation, antithrombotic medications)

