#### 9.3.2 Patient 12 week end of observation questionnaire

For evaluable patients providing consent and for whom a completed baseline questionnaire has been received by the DSRU, at least 13 weeks after starting antiplatelet therapy, a second questionnaire will be systematically generated to collect clinical information from the specialist HCP relevant to start of observation and any clinical events of medical interest as recorded in the medical charts during the first 13 weeks (to ensure a full 12 week observation period post index date for each patient).

Data obtained from the 12-week end of observation questionnaire will include: Version 7 Date: 30/08/2017

- Additional information on anticoagulation treatment regimen:
  - Details of prior use of oral and parenteral anticoagulant and antiplatelet therapy (e.g. thienopyridines, aspirin, glycoprotein IIb/IIa inhibitors, heparins) in the past 12 months if known
  - Treatment regimen during the 12 weeks observation period
  - If study treatment regimen has changed: date and reason for change, details of transition plan to alternative; if required, details of reversal of anticoagulation therapy and management of bleeding complication
- Recent (< 4 weeks prior to index date) and concomitant medications (at index or during treatment):
  - not recommended for concomitant use (including azole antimycotics [e.g. ketoconazole] and HIV protease inhibitors)
  - to be used with caution (including fluconazole, strong CYP3A4 inducers, strong P-gp inhibitors, non-steroidal anti-inflammatory drugs (NSAIDs), acetylsalicylic acid, oral steroids, hormone and oral contraceptive therapy, platelet aggregation inhibitors or other antithrombotic agents)
- Medical history relevant for important potential, identified and special risks of interest (plus dates of first diagnosis/report)
- Specific information on renal function status and creatinine clearance at index date and any changes during 12 week observation period
- Specific information on hepatic disorders present at index date and any recent abnormal liver function tests
- Event reports including selected risks of interest (Table 3)
- Cause and date of death (if died) in the first 12 weeks after starting treatment;
- Behaviours prior to and/or starting treatment (e.g. smoking, alcohol/substance misuse)

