#### 9.7.1 To quantify the cumulative incidence (risk and rate) of major bleeding according to the TIMI classification of non-CABG Related Bleeding (Table 1) occurring in the 12 week observation period, overall and stratified by intracranial, gastrointestinal and urogenital bleeding sites.

The following relates to Section 8.2 primary objective and relates to haemorrhage within gastrointestinal and urogenital organ sites (which meets the criteria for a TIMI major non CABG related bleed) and all intracranial sites (as defined in Table 1). This time to event analysis will be performed separately for the rivaroxaban exposed cohort and the contextual cohort, as defined according to exposure at index (date antiplatelet therapy was prescribed as part of the acute management of the ACS).

<sup>1 In the event of a change in treatment resulting in a switch in treatment group, person-time contributed will be censored at the time of switching, thus analysis will not be 'intention to treat' as this is an observational study.

For each cohort, for whom acute management of ACS applies, the numerator for this analysis will comprise of adjudicated incident major bleeding events (overall and stratified by intracranial, gastrointestinal and urogenital bleeding sites) defined according to primary objective that were reported during the 12 week observation period post index date. These adjudicated events will have been reviewed by an expert panel using all available information from SCEM questionnaires, follow-up and any additional documentation. Patients for whom events were misreported will be excluded from the analysis (events will be excluded, but denominator data will still be included); patients for whom events were misclassified will be reclassified as appropriate. In addition, for each cohort, for the three organ sites specified in the primary outcome, counts of each of the individual components of the TIMI major non CABG related bleeding criteria will be summarised. Where an individual has one or more criterion for an individual organ site of interest, counts will also be summarised – in such individuals the first report will be regarded as the incident event. Since SCEM data are right censored, the cumulative incidence (risk and rate) of the primary outcomes reported during treatment within the 12 week observation period will be calculated using survival analysis methodology.

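### The panel that decides which primary bleeds count works from records that show the treatment, and no masking is stated

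*Protocol*

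**What the plan says.** Section 8.2 applies the primary outcome to both groups: "Both the primary and secondary objectives relate to the rivaroxaban cohort and the contextual comparator (reference) cohort". Section 9.7.1 then specifies, for each cohort, that "the numerator for this analysis will comprise of adjudicated incident major bleeding events". The panel's material is described in one sentence: "These adjudicated events will have been reviewed by an expert panel using all available information from SCEM questionnaires", to which the sentence adds follow-up and other documents.

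The panel's decisions change the count. Where it finds an event misreported, "events will be excluded, but denominator data will still be included". Otherwise, "patients for whom events were misclassified will be reclassified as appropriate".

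The questionnaires named as the panel's source carry the treatment. The baseline form (section 9.3.1) records "Which anticoagulant/antiplatelet regimen was prescribed and start date". The specialist's 12-week form (section 9.3.2) records "Treatment regimen during the 12 weeks observation period" and, where relevant, how anticoagulation was reversed. The abridged GP form (section 9.3.3) also asks for the regimen received. The protocol does not say that any of this is withheld from the panel.

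**The concern.** Some parts of the TIMI definition in Table 1 need judgement: whether an intracranial haemorrhage was symptomatic, whether a death resulted directly from bleeding, and whether a bleed was related to CABG. A reviewer who knows that the patient took an anticoagulant on top of antiplatelet therapy may accept a borderline case more readily, or may scrutinise it harder. Either way, the standard of proof can differ between cohorts.

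This bears on the rivaroxaban incidence itself, which is the main product of the study. It also bears on how that incidence is read, because section 9.1 says the second cohort is there to put the rivaroxaban observations into context through comparison. Section 9.2.2 relies on both cohorts having the same data collection methods. The limitations in section 9.9 discuss misclassification, but not grading by people who know the exposure.

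**Working it through.** **What the panel can see and change**

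1. The primary numerator contains only events that passed the panel (9.7.1).
2. The panel works from the questionnaires, follow-up and other documents, with nothing excluded (9.7.1).
3. All three questionnaires hold the regimen (9.3.1, 9.3.2, 9.3.3).
4. The panel can delete or regrade an event while the patient stays in the denominator (9.7.1).

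Points 1 to 3 together mean that treatment is visible when events are graded, unless someone departs from the text. Point 4 means that the grading sets the estimate.

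**The plan's own figure**

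Inputs from section 9.5: p = 0.005, half-width d = 0.004, 95% confidence.

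n = 1.96² × p(1 − p) / d² = 3.8415 × 0.004975 / 0.000016 = 1194.5

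The stated 1193 is within 2 patients of this, so it reproduces.

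**Weight of one decision, rivaroxaban cohort**

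- Expected events: 1193 × 0.005 = 5.97, about 6.
- One event: 1/1193 = 0.084 percentage points.
- Relative to the expected risk: 0.084 / 0.5 = 17%, about one sixth.
- Relative to the planned half-width: 0.084 / 0.4 = 21%, about one fifth.

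| Confirmed events | Incidence | Exact 95% CI |
|---|---|---|
| 5 | 0.42% | 0.14% to 0.98% |
| 6 | 0.50% | 0.19% to 1.09% |
| 7 | 0.59% | 0.24% to 1.21% |

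The site strata are thinner. From the 0.1%, 0.3% and 0.1% in section 9.5, the expected counts are 1.2 intracranial, 3.6 gastrointestinal and 1.2 urogenital events. Section 9.7.1 also asks for at least five reports before the hazard is modelled, so two rejections out of six (leaving four) would bring the confirmed count below that number.

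**Illustration across cohorts**

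The protocol gives no comparator rate. Suppose, purely as an assumption, that each cohort of 1193 has 6 true events. One error in each direction gives 7 against 5, a ratio of 1.4. Two in each direction give 8 against 4, a ratio of 2.0. Nothing in the protocol says how often borderline cases will arise, so these figures show sensitivity and do not predict bias.

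**The case against.** The strongest reply has five parts.

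- **The text does not say the panel is unmasked.** This is correct: it lists sources and does not describe a case pack, and a charter or SAP that is not shown could add redaction. But redaction would narrow what 9.7.1 tells the panel to use, so the sentence itself needs changing.
- **No contrast is planned.** This also stands. The time-to-event analysis is run separately by cohort, no hazard ratio or between-cohort test of bleeding is specified, and the ENCePP checklist says no formal hypotheses are tested. A reader might infer that the panel would produce a false treatment effect in a formal comparison; the protocol plans no such comparison. What remains is the effect on each incidence and on an informal reading of the two together.
- **The criteria are partly objective.** Overt bleeding counts as major only with a haemoglobin drop of at least 5 g/dL, and fatal bleeding has a 7-day limit. This narrows the room for judgement without closing it.
- **There is a check.** Section 9.7.1 plans an analysis of all reported major bleeds regardless of adjudication, and counts of each TIMI component by cohort. Set beside the primary result, that analysis would show the panel's net effect. Its stated aim is incomplete cases, however. Removals and upgrades can cancel, and it gives no estimate graded without knowledge of exposure.
- **Treating clinicians know the treatment anyway.** They do, and masking the panel leaves bias in their reporting untouched. A central panel is nevertheless a step where masking is feasible.

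**Conclusion.** The point holds as a moderate weakness in a stated procedure. As section 9.7.1 is written, the panel can know the cohort while it decides which primary events to keep, remove or regrade. With about 6 events expected in the rivaroxaban cohort, each decision is worth 0.084 percentage points, about one sixth of the expected risk. The direction of any bias is unknown.

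This rests on the 0.5% risk and the full 1193 patients from section 9.5, and on the panel using the questionnaires as received. A reader might carry the figure of 6 events over to the contextual cohort, but section 9.5 gives 0.5% only for patients on rivaroxaban. Nor does the protocol give this panel the BARC grading or the drug-relatedness assessment of section 9.7.5, so the point is confined to the TIMI-defined primary events.

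**What to change.** Amend section 9.7.1 so that:

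- the panel assigns TIMI category and bleeding site from case packs in which drug name, cohort and regimen are redacted, with details of anticoagulant reversal also removed where feasible;
- treatment is disclosed only after grading is recorded;
- the numbers of confirmed, reclassified and rejected events are reported by cohort.

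The sample size does not change. The cost is one or two sentences in the protocol and modest clerical work per pack; the number of packs cannot be stated, because the protocol gives no expected number of reported bleeds. Masking will be incomplete where a narrative reveals the treatment, and reporting by clinicians who know the exposure remains a limitation that section 9.9 should name.

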For each individual case, relevant person-time will be estimated according to duration of observation up to event date. For each individual non-case, relevant person-time will estimated by either exit date – index date; or censor date – index date; or stop date (+ 2 days ) – index date. For each cohort separately, a semi-parametric time-dependent Cox Proportional Hazards regression model will be used to estimate the crude cumulative incidence over the 12 week observation period.

Non-parametric Kaplan-Meier plots will be presented to describe time-to event as well as smoothed estimates of the empirical hazard function to describe how the crude baseline risk of the event changes over time.

Estimates of the hazard function will also be modelled to determine whether the baseline hazard (risk) of the event increases or decreases with time. A constant hazard over time may be consistent with a background (not caused by the drug) event rate, whereas a non-constant hazard over time may be an indicator of a drug-event relationship. The null hypothesis that the hazard rate of the selected event in patients will be constant during the 12 week period following the start of treatment will be tested

<sup>1 This excludes patients prescribed rivaroxaban 2.5mg for non-ACS related indications

<sup>2 Censor date = date of loss to follow-up

<sup>3 2 days allocated to person-time to account for half-life of drug

Version 7 Date: 30/08/2017

by fitting a parametric time to event model (e.g. Weibull). Such models have a shape parameter that indicates whether the hazard is significantly increasing or decreasing over time. At least five reports of an event are deemed necessary for modelling purposes.

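### Section 9.7.1 gives two conflicting numerators for the primary bleeding outcome, and its person-time rules for cases and non-cases do not settle which applies

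*Protocol*

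**What the plan says.** All of the following is in Protocol section 9.7.1.

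- **First numerator.** Adjudicated incident major bleeds "defined according to primary objective that were reported during the 12 week observation period post index date". This sentence has no on-treatment limit. It fits the primary objective in section 8.2 and the 12-week censoring of events in section 9.1.
- **Second numerator.** The last sentence of the same paragraph says that survival methods will estimate "the cumulative incidence (risk and rate) of the primary outcomes reported during treatment within the 12 week observation period".
- **Person-time, cases.** "For each individual case, relevant person-time will be estimated according to duration of observation up to event date". No stop-date limit is stated.
- **Person-time, non-cases.** The rule opens "For each individual non-case, relevant person-time will estimated by either exit date" and offers loss to follow-up or stop date plus 2 days as alternatives, all measured from index. It does not say that the earliest applies. A footnote explains the allowance: "2 days allocated to person-time to account for half-life of drug".
- **Switching.** A footnote censors person-time when a patient changes treatment group and says that the analysis is not by intention to treat. It is not limited to non-cases.

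No sentence says whether a bleed more than 2 days after stopping, but within 12 weeks, is an event.

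**The concern.** Take two patients who both stop in week 3. One bleeds in week 8 and the other never bleeds. With the first numerator and the person-time rules as written, the first is an event with 8 weeks at risk and the second contributes 3 weeks and 2 days. The end of follow-up then depends on the outcome. Survival methods need a censoring rule that can be applied without knowing whether the patient later bleeds.

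The consequence would be an upward bias in the primary rate, larger in a cohort where more patients stop. The hazard shape would also be affected, because late risk sets would lose stopped non-bleeders and keep late bleeders. Section 9.7.1 reads a non-constant hazard as a possible sign of a drug-event relationship.

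With the second numerator the problem all but disappears. The primary estimate is therefore not defined for off-treatment bleeds, and the choice could be made after the events have been seen.

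**Working it through.** **Inputs from the protocol.** Expected 12-week risk 0.5%, precision ±0.4% and 1193 patients per cohort (section 9.5); 12 weeks = 84 days; 2-day allowance (section 9.7.1).

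**Assumptions, not in the protocol.** A fraction f of patients stops (10%, 20% or 30%), at day s = 14 or 42. The bleeding hazard is constant on treatment and, after stop + 2 days, is r = 0.5 or 1 times that value.

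**1. The plan's own figure.** n = 1.96² × 0.005 × 0.995 / 0.004² = 1194.5, against 1193 stated. It reproduces to about 0.1% and does not depend on this point. Expected events per cohort: 1193 × 0.005 = 5.97.

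**2. Hazard.** λ = −ln(0.995)/84 = 5.967 × 10⁻⁵ per day, or 0.418 per 1000 patient-weeks. This is the matched on-treatment rate.

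**3. Person-time per patient.** Let c = s + 2. Because the risk is small, to a close approximation:

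- on-treatment days: P_on = (1 − f) × 84 + f × c
- off-treatment days: P_off = f × (84 − c)
- events under the 12-week numerator: λ × (P_on + r × P_off)
- person-time under the literal rule: about P_on, since the few off-treatment cases add almost nothing

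Hence literal rate / matched on-treatment rate = 1 + r × P_off / P_on, and literal rate / matched 12-week rate = 84 / P_on.

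Smallest case (f = 10%, s = 42, r = 0.5): P_on = 75.6 + 4.4 = 80.0, P_off = 4.0, ratio = 1 + 2.0/80.0 = 1.025.

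Largest case (f = 30%, s = 14, r = 1): P_on = 58.8 + 4.8 = 63.6, P_off = 20.4, ratio = 1 + 20.4/63.6 = 1.32.

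The table gives the ratios from the exact exponential model, which differ from these approximations by about 0.001 at most.

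| Stop by week 12 | Stop day | P_on | P_off | vs on-treatment, r = 0.5 | vs on-treatment, r = 1 | vs full 12 weeks |
|---|---|---|---|---|---|---|
| 10% | 42 | 80.0 | 4.0 | 1.02 | 1.05 | 1.05 |
| 10% | 14 | 77.2 | 6.8 | 1.04 | 1.09 | 1.09 |
| 20% | 42 | 76.0 | 8.0 | 1.05 | 1.11 | 1.11 |
| 20% | 14 | 70.4 | 13.6 | 1.10 | 1.19 | 1.19 |
| 30% | 42 | 72.0 | 12.0 | 1.08 | 1.17 | 1.17 |
| 30% | 14 | 63.6 | 20.4 | 1.16 | 1.32 | 1.32 |

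If no bleeds occur after stop + 2 days (r = 0), the ratio to the on-treatment rate is 1.00.

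**4. Events that turn on the reading.** 1193 × λ × r × P_off. Smallest: 1193 × 5.967 × 10⁻⁵ × 0.5 × 4.0 = 0.14. Largest: 1193 × 5.967 × 10⁻⁵ × 1 × 20.4 = 1.45 (1.448 in the exact model). That is roughly 0.1 to 1.4 of about 6 events per cohort.

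**5. During-treatment numerator.** Cases end at the bleed and non-cases at exit, loss or stop + 2 days. The ratio is 1.00. If bleeds in the 2 added days are not counted, a small downward mismatch remains. At 20% stopping it is 0.2 × 2 = 0.4 day out of 70.4 to 76.0, or 0.5–0.6%.

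These figures are for the rate. The estimated risk would move in the same direction under the literal rule, because the late risk sets shrink.

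**The case against.** The strongest reply is that the text leans towards an on-treatment analysis. The sentence that says what the survival analysis estimates restricts it to outcomes "primary outcomes reported during treatment within the 12 week observation period", and the switching footnote disclaims intention to treat. Section 9.7.4 likewise counts events during treatment, and its seven-day sensitivity analysis extends numerator and denominator together. On that reading section 9.7.1 is ordinary on-treatment censoring. The 2 days can naturally be taken as exposed time for events as well as for person-time.

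Much of this stands. A reader might infer that the primary rate is inflated as planned. The documents do not support that, because it follows from one of two stated numerators only. A reader might also infer a distorted comparison between cohorts. Section 9.7.1 analyses them separately and Annex 2 states that no formal hypothesis is tested, so only an informal contextual reading could be affected. The possible shift is also small beside the planned precision: ±0.4% on 0.5% is ±80% in relative terms.

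The reply does not remove the contradiction. The first sentence is an explicit definition of the numerator, and it agrees with sections 8.2 and 9.1. The switching footnote covers a change of treatment group, not stopping. Section 9.7.4 shows how the authors handle a related analysis but does not govern the primary one. Nor is this detail merely left to a statistical analysis plan, since the protocol itself fixes both versions.

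**Conclusion.** The point holds as an unresolved contradiction. Section 9.7.1 states two numerators, and its person-time rules are coherent only with the during-treatment one.

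If the 12-week numerator is applied literally, the rate is biased upward, by about 2–9% at 10% stopping, 5–19% at 20% and 8–32% at 30%, against the matched on-treatment rate. If the during-treatment numerator governs, the inflation is essentially nil. The true size cannot be fixed from the protocol, because the stopping proportion, stop time and off-treatment hazard are all assumed here.

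With about 6 events expected per cohort, even one bleed that depends on the reading is visible in the primary result. It should be fixed, but it does not show that the planned result is wrong.

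**What to change.** Reconcile the two numerator sentences in section 9.7.1 and state one end of follow-up for cases and non-cases alike: the earliest of event, stop date plus 2 days, switch of treatment group, loss to follow-up, death or 12 weeks after index. Count a bleed only if it falls on or before that date, so that the 2 added days can hold events as well as person-time.

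Optionally, add a separately labelled analysis that follows everyone for the full 12 weeks regardless of stopping, with all bleeds counted and all person-time included.

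The cost is a few sentences and minor programming, with no new data collection and no change in sample size. The downside is that off-treatment bleeds leave the main numerator; the optional analysis would keep them in view.

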#### 9.5 Study Size

The ability to detect an adverse event is dependent on the expected incidence rate of the adverse event in those exposed to the drug, the background rate in those not exposed to the drug, and the total number of patients.

Where studies, such as clinical trials, have already estimated the impact of the exposure on the outcome of interest, the objective should be to estimate the magnitude of the effect as precisely as possible (21). As such, in this study it is more appropriate to choose a sample size that will yield a confidence interval of a predefined width for those identified risks defined within the primary outcome which are of greatest clinical and medical importance i.e. major bleeding outcomes. Table 4 displays the samples sizes (95% confidence intervals) across a range of expected incidences and levels of precision. From rivaroxaban clinical trial data, the cumulative incidence risk of first occurrence of adjudicated major bleeding events (intracranial, GI and urogenital) in patients taking rivaroxaban for secondary prevention after ACS over the first 12 weeks of treatment was approximately 0.5% (0.1%, 0.3% and 0.1%). Thus in this population of patients with ACS treated with rivaroxaban, in order to estimate the expected (true) cumulative incidence of primary outcomes of major bleeding events of 0.5% within +/- 0.4%, we would ideally need a sample size of 1193 patients (Table 4). An equivalent number of patients within the contextual comparator cohort is desirable.

Incidence									
from RCT	Precision								
(%)	0.2%	0.3%	0.4%	0.5%	0.6%	1%	2%	3%	5%
0.10	958	426	240	153	107	38	10	4	2
0.20	1913	851	479	307	213	77	19	9	3
0.30	2864	1275	718	459	319	115	29	13	5
0.40	3812	1698	956	612	425	153	38	17	6
0.50	4755	2119	1193	764	531	191	48	21	8
0.70	6631	2958	1666	1067	741	267	67	30	11
0.80	7564	3376	1902	1218	846	305	76	34	12
1.00	9418	4208	2371	1519	1055	380	95	42	15
1.25	11716	5241	2955	1893	1315	474	119	53	19
1.50	13991	6267	3535	2265	1574	567	142	63	23
2.00	18475	8296	4684	3003	2087	752	188	84	30
3.00	27187	12268	6938	4452	3096	1117	279	124	45
4.00	35566	16126	9135	5866	4081	1473	369	164	59
5.00	43627	19871	11276	7246	5043	1821	456	203	73

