# Table 4.Sample sizes of evaluable patients required to estimate the
expected (true) cumulative incidence of a specified adverse event
with 95% confidence intervals of different precisions (0.2% to
5%).

#### 9.6 Data Management

#### 9.6.1 Data Processing

Specialist HCP/ GP/ patient identifiable information will be stored within a unique database. All original documents and individual correspondence from HCPs will be stored for 15 years at the DSRU, with considerable care taken to preserve patient confidentiality (see below).

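### The Cox model fixed for the site-specific primary incidence gives no usable interval for a site with no events, about a 30% chance each for intracranial and urogenital bleeding in the rivaroxaban cohort

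*Protocol*

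**What the plan says.** The primary objective (Protocol 8.2) is the cumulative incidence, as risk and rate, of TIMI major bleeding unrelated to CABG over 12 weeks, "overall and stratified by the following bleeding sites": intracranial, gastrointestinal and urogenital. It applies to both cohorts.

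Section 9.7.1 takes as its numerator "adjudicated incident major bleeding events (overall and stratified by intracranial, gastrointestinal and urogenital bleeding sites". It calls for survival methods because the data are right censored, and it names the estimator: "For each cohort separately, a semi-parametric time-dependent Cox Proportional Hazards regression model will be used to estimate the crude cumulative incidence". Kaplan-Meier appears only as plots that describe time to event. The same section sets a minimum of five reports for modelling, directly after the Weibull test of hazard shape. It does not say what to do below five.

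Section 9.5 gives the planning risk for the three sites combined, then for intracranial, gastrointestinal and urogenital bleeding in turn: it "was approximately 0.5% (0.1%, 0.3% and 0.1" percent. The aim is to estimate a "cumulative incidence of primary outcomes of major bleeding events of 0.5% within +/- 0.4" percentage points, for which "we would ideally need a sample size of 1193 patients (Table 4"). For the other cohort, "An equivalent number of patients within the contextual comparator cohort is desirable".

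**The concern.** The incidence is crude and each cohort is fitted alone, with no covariate named for the main estimate. The Cox model then has no regression coefficient to estimate and reduces to its baseline hazard. That hazard exists only where events occur. Two of the three primary sites are expected to yield about one event each, so an empty site is an ordinary outcome, and one that includes the most serious type of bleed.

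The study is sized on the width of a confidence interval, so the interval is what it is meant to deliver. For an empty site the useful safety statement is the largest risk the data still allow. The named method cannot supply it, and a zero without a bound can be read as reassurance that the data do not give.

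**Working it through.** **Inputs (Protocol 9.5).** Combined risk 0.5%; site risks 0.1%, 0.3% and 0.1%; half-width 0.4 percentage points; n = 1193; 95% confidence.

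**The plan's own figure.** The normal-approximation formula is n = z² p(1−p)/d² = 1.96² × 0.005 × 0.995 / 0.004² ≈ 1194.5. A finite-population correction with an assumed population of 1,000,000 gives 1193.03, matching 1193. The same correction gives 4755.1, 2119.0 and 763.9 for the neighbouring entries 4755, 2119 and 764 of the 0.5% row. The figure is reproduced; it rests on the combined risk only.

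**Chance of no event.** Expected events = np; P(0) = (1−p)^n, with n = 1193.

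| Outcome | p | Expected events | P(0) |
|---|---|---|---|
| Intracranial | 0.1% | 1.19 | 30.3% |
| Urogenital | 0.1% | 1.19 | 30.3% |
| Gastrointestinal | 0.3% | 3.58 | 2.8% |
| Three sites combined | 0.5% | 5.97 | 0.25% |

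If intracranial and urogenital events are treated as independent, the chance that at least one of the two sites is empty is 1 − (1 − 0.303)² = 51%.

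**Sensitivity to rounding.** A value printed as 0.1% could lie between 0.05% and 0.15%. P(0) is then 0.9995^1193 = 55% or 0.9985^1193 = 17%.

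**Sensitivity to cohort size.** At 0.1%, P(0) is 36.8% for n = 1000, 40.6% for n = 900 and 54.9% for n = 600. Early censoring also lowers the expected count.

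**Contextual cohort.** The protocol gives no event rate. If its site risk were 0.05% (assumption), P(0) would be 55% per site.

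**What the estimator returns with no event.** The partial likelihood has no terms. The Breslow cumulative hazard is a sum over event times, so it and its variance are both 0, and the incidence 1 − exp(−0) is 0. A log-log interval needs log(0) and is undefined. Kaplan-Meier does no better: the curve stays at 1 and the Greenwood variance is 0.

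**What the data would support.** With 0 events and full follow-up, person-time is 1193 × 12 = 14,316 patient-weeks.
- The exact two-sided 95% Poisson upper limit is −ln(0.025)/14,316 = 3.689/14,316 = 0.258 per 1000 patient-weeks.
- As a 12-week risk this is 1 − exp(−12 × 0.000258) = 0.31%. The exact binomial limit for 0/1193 is also 0.31%.

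**With one event.** The cumulative hazard is about 1/1193 = 0.0838%. A log-log interval multiplies and divides it by exp(1.96) = 7.10, giving 0.012% to 0.59%. This is usable and positive.

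**The case against.** The strongest reply is that the protocol names an estimator but no interval method, and interval methods are commonly left to the analysis plan, which could add an exact limit without contradicting 9.7.1. That is true, and it rules out any claim that the final report will show an unbounded zero. It does not remove the point. The estimator the protocol fixes supplies no interval in a likely scenario, and nothing in the text offers a fallback. The five-report minimum follows the Weibull test. If it were read as covering every model, the chance of fewer than five events would be 99.2% for each 0.1% site, 71.1% for gastrointestinal and 28.9% combined. Crude risks and incidence densities are described in 9.7.4 for secondary and exploratory events.

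A reader might also infer three stronger things that the document does not support.

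- **Impossible intervals with one or two events.** A plain normal interval for 1/1193 runs from −0.08% to 0.25%, but the protocol never chooses that interval, and a log-log interval stays positive.
- **A wrong sample size or a compromised overall result.** The 1193 is justified on the combined 0.5%, where an empty result has a chance of about 0.25%.
- **A simple binomial proportion should be the primary risk estimate.** Section 9.7.1 chose survival methods because follow-up is censored: person-time ends at switching, at loss to follow-up, or shortly after stopping. A simple proportion counts patients censored early as event-free for 12 weeks and biases the risk downward.

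Finally, a point estimate of zero is correct when no event is seen, and the component counts that 9.7.1 also requires would appear beside it. Only the missing bound is at fault.

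**Conclusion.** The point holds for the site-specific primary results when a site has no event. In the rivaroxaban cohort at full size the chance is about 30% for each of intracranial and urogenital bleeding. That figure rests on approximate trial risks (range 17% to 55% from rounding alone), on 1193 evaluable patients, and on follow-up close to complete. The consequence is the loss of an upper bound of about 0.31% that the data would support. Gastrointestinal bleeding is rarely affected (2.8%). This is a worthwhile, inexpensive correction to a method the protocol states; it does not threaten the study's design.

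**What to change.** In 9.7.1, for each site and cohort:

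- Report the event count and the incidence rate on observed person-time, with an exact two-sided 95% Poisson interval.
- When there are no events, give the upper limit and convert it to a 12-week risk by 1 − exp(−12 × weekly rate). State that the conversion assumes a constant hazard.
- Where events occur, keep the censoring-adjusted survival estimate of cumulative incidence, with an interval that cannot go below zero, such as log-log. Do not replace it with a simple proportion.
- Say whether the five-report minimum covers only the Weibull model or the Cox fit as well.

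The counts and person-time are already defined in 9.7.1, so no new data are needed. The cost is one extra analysis line and intervals that look wider. The constant-hazard assumption behind the converted risk cannot be checked when no events are seen.
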